
evaluated as a predictor of outcomes after cardiac surgical procedures. Finally, pilot data will be obtained on whether two novel risk factors (frailty and depth of anesthesia) might be associated with postoperative delirium. Brain injury from cardiac surgery is an important source of operative mortality, prolonged hospitalization, increased health care expenditure, and impaired quality of life. Developing strategies to reduce the burden of this complication has wide public health implications and is within the mission of the NHLBI.

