In **Aim 5**, we will test the hypothesis that frailty is associated with postoperative delirium. The primary outcome will be the development of delirium at any time, as measured by CAM or CAM-ICU and coded as a binary variable. Secondary outcomes will be delirium severity from the DRS-R-98 scale. Bivariable and multivariable logistic regression analysis will be used to determine if frailty is associated with postoperative delirium. We will also test the hypothesis that frailty is associated with decreased function after cardiac surgery. The primary outcome will be proportion of patients with >1 IADL decline. Secondary outcomes will be change in gait speed and grip strength. Bivariable and multivariable linear and logistic regression analyses will be used. For each of these analysis, covariates to include in the model will be selected using a priori evidence, and may include age, gender, race, baseline cognitive status, education, medications, and

type of surgery. We will also consider propensity score analysis to account for important confounding.

**Aim 6:** *To determine whether depth of anesthesia in frail patients is a modifiable risk factor for delirium and functional decline after cardiac surgery.*

In **Aim 6**, we will compare cumulative time of BIS<45 in frail vs. non-frail patients using bivariable and multivariable linear regression. The cumulative time of BIS<45 will also estimate the amount of potential anesthetic overdose in all patients.

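### Aim 6 asks whether anaesthetic depth in frail patients is a modifiable risk factor for delirium and functional decline, but neither outcome enters its planned analysis

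*Combined protocol and SAP*

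**What the plan says.** Aim 6 appears in Study Statistics as: "To determine whether depth of anesthesia in frail patients is a modifiable risk factor for delirium and functional decline after cardiac surgery". Two outputs follow. The first is a linear regression, unadjusted and adjusted: "we will compare cumulative time of BIS<45 in frail vs. non-frail patients". The second is descriptive: "The cumulative time of BIS<45 will also estimate the amount of potential anesthetic overdose in all patients".

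The Abstract Summary says that pilot data will be obtained on "whether two novel risk factors (frailty and depth of anesthesia) might be associated with postoperative delirium".

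Aim 5, directly above, does model delirium, but with a different exposure: "Bivariable and multivariable logistic regression analysis will be used to determine if frailty is associated with postoperative delirium". It treats functional decline in the same way. Its covariates "may include age, gender, race, baseline cognitive status, education, medications, and" type of surgery; BIS is not named.

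The Depth of Anesthesia part of the Background gives a narrower purpose for the BIS work. The range of BIS values in cardiac surgery is not known, the study will describe it in frail and non-frail patients, and more time below 45 is expected in the frail. The Objectives list ends at Aim 5.

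**The concern.** The aim has depth as the exposure and delirium and function as the outcomes. The planned model has depth as the outcome and frailty as the predictor. A team that follows the plan exactly will finish with no estimate of the association that the aim and the abstract describe, although it will hold the data for one.

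The wording adds two demands that the analysis does not meet. *In frail patients* calls for an estimate within that group, or a frailty-by-depth interaction. *Modifiable* implies that changing depth would change outcome, yet depth is only recorded here. Randomisation concerns blood pressure.

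The Background already says that more low-BIS time in frail patients would support developing a protocol to alter depth. Placed under Aim 6 as now worded, a frail versus non-frail difference in BIS time could be taken as evidence about delirium, which it is not.

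**Working it through.** **1. Is there a figure to reproduce?** No. The sample-size text covers the composite, the cognitive Z-score and delirium by randomised arm (Aim 4). It gives no N, effect size or power for Aim 6.

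**2. Aim against analysis.**

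| | Exposure | Outcome | Population |
|---|---|---|---|
| Aim 6 as worded | Depth of anaesthesia | Delirium, functional decline | Frail |
| Abstract Summary | Depth of anaesthesia (and frailty) | Delirium | Not restricted |
| Aim 6 regression | Frailty | BIS<45 time | Frail and non-frail |
| Aim 6 second output | None | BIS<45 time | All |
| Aim 5 | Frailty | Delirium, IADL decline, gait speed, grip strength | All |

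The analyses for Aims 1 to 4, the Missing data section and the Statistical Analysis Plan section contain no BIS term. No row or section pairs BIS as exposure with delirium or function as outcome.

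**3. What the planned contrast can show.** Delirium is not in the model, so the result cannot depend on how delirium relates to BIS. An illustrative simulation makes this concrete. Its inputs are assumed: 200,000 patients, 30% frail, mean BIS<45 time of 60 minutes in non-frail and 80 in frail patients, SD 40.

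| True odds ratio per SD of BIS<45 time | Planned contrast (min) | Delirium model, all patients, with frailty | Delirium model, frail only |
|---|---|---|---|
| 1.0 | 20.2 | 1.00 | 1.00 |
| 1.5 | 20.2 | 1.50 | 1.52 |
| 2.0 | 20.2 | 2.00 | 1.98 |

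**4. Are the data there?** Yes. BIS is recorded during surgery. Delirium is assessed with CAM or CAM-ICU on three of the first four postoperative days. Frailty testing, with the IADL scale, is scheduled before surgery, at 4 to 6 weeks and at 1 year.

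**5. Precision if the missing model were fitted.** Inputs:
- N = 2 × 180 = 360, the projected number with careful delirium assessment. The documents do not say how many of these also have BIS data; I assume all.
- Delirium rate 40%. Aim 4 assumes 50% in controls and a 40% reduction: 0.50 × (1 − 0.40) = 0.30, and (0.50 + 0.30)/2 = 0.40.
- Two-sided 5% and 80% power: 1.96 + 0.84 = 2.80.

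Detectable log odds ratio per SD = 2.80 / √[N × p(1 − p) × (1 − R²)], where R² is the share of the variance in BIS<45 time explained by the covariates. The values of R² and the frail proportion below are assumptions; the documents give neither.

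| Setting | Calculation | Odds ratio per SD |
|---|---|---|
| All 360, unadjusted | 2.80/√(360 × 0.24) = 0.301 | 1.35 |
| All 360, R² = 0.30 | 0.301/√0.70 = 0.360 | 1.43 |
| All 360, R² = 0.50 | 0.301/√0.50 = 0.426 | 1.53 |
| Frail only, 40% (144), unadjusted | 2.80/√(144 × 0.24) = 0.476 | 1.61 |
| Frail only, 30% (108), unadjusted | 2.80/√(108 × 0.24) = 0.550 | 1.73 |
| Frail only, 20% (72), unadjusted | 2.80/√(72 × 0.24) = 0.674 | 1.96 |

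Adjustment within the frail group would raise the last three rows further. An interaction would need larger effects still.

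**The case against.** The best defence is that the analysis is sound and the sentence above it is at fault. The Background sets out a descriptive study of BIS values in frail and non-frail patients, and the regression delivers exactly that. Rewording the aim would then be a complete and cheaper repair. Much of this stands: the frail versus non-frail comparison is a legitimate analysis and should stay. It does not dispose of the point, because the Abstract Summary separately offers data on depth and delirium, and rewording alone would withdraw that offer.

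The second defence is scale. Aim 6 is outside the Objectives, is not powered, and in the abstract is only pilot work. That stands in full. A reader might infer that the trial's main conclusions, or Aims 1 to 5, are compromised. They are not: none of those analyses uses BIS, and nothing is lost for good, since the data are collected in any case.

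The third is that Aim 5's covariate list is open-ended, so BIS could be added there. The list does not name it, and an unplanned covariate in a model built for frailty is not a pre-specified estimate for depth.

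**Conclusion.** The mismatch is established from the text alone and needs no assumption: as planned, Aim 6 yields no information on whether anaesthetic depth relates to delirium or functional decline. Even with the right model, the data could support an association, not modifiability.

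It is worth correcting, but it is a defect in a peripheral, in effect exploratory, aim. It is also tempting to say that the study could readily detect an odds ratio of 1.35. The documents do not support that as the precision for this aim: the figure is unadjusted, uses all 360 projected patients rather than the frail, and assumes that each has both measurements. About 1.43 to 1.53 is more realistic for an adjusted estimate in all patients, and about 1.6 to 2.0, before adjustment, for the frail group, on the assumed covariate R² and frail proportions.

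**What to change.** Preferred: pre-specify, labelled exploratory,
- a model of delirium (logistic or modified Poisson) and a model of IADL decline, each on BIS<45 time, frailty and their interaction;
- adjustment for anaesthesia duration, age and baseline cognition. Duration matters because longer cases can accumulate more minutes below 45;
- the BIS estimate within frail patients, reported with its confidence interval.

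In the aim, replace the modifiable-risk-factor wording with *is associated with*. Keep the frail versus non-frail BIS contrast as descriptive.

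Alternative, if the models are not added: reword Aim 6 and the corresponding sentence of the Abstract Summary to the descriptive question in the Depth of Anesthesia background.

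The cost is one or two extra models on BIS, delirium and IADL data already being collected, plus the wording change. The drawback is imprecise estimates in frail patients, which must not be presented as confirmatory.

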### ***Rapid Dissemination of Clinical Research***

A major objective of this study is to disseminate new information to the medical and lay communities. We propose to fulfill this aim by presentations at national and international meetings and conventional publications in the medical literature. Full results of the study will be published as soon as possible, consistent with principles of peer-reviewed publication. National meetings of the AHA, American Stroke Association, Society of Thoracic Surgeons, and the Society of Cardiovascular Anesthesiologists are excellent venues for presenting clinical study results. We will continue to use MedDium, LLC ([name]) for a Web portal that provides the NIH and public with visibility into program activities and major scientific discoveries. Finally, the media relations department at Northwestern University will be utilized to coordinate press releases of study trial results as they become available.

Secondary outcome variables.

Included in Primary outcome variables (above).

Statistical plan including sample size justification and interim data analysis.

Sample size calculations are based on detecting differences in the proportion of patients with an adverse neurologic outcome (DWI lesion, stroke, or cognitive decline 4 to 6 weeks after surgery) between the Control and Intervention groups. We expect that approximately 45% of subjects in the Control Group will experience an adverse neurologic outcome after surgery based on the preliminary data analysis of outcomes of 176 patients. In comparison, we expect that the proportion of the Intervention Group that experiences adverse neurologic outcomes will be reduced by 40-45% (e.g. The frequency of neurologic adverse events will be between 25% and 27%). This magnitude of reduction in the frequency of the composite outcome is within the range that is considered to be clinically important effect (20% to 45% reduction from control frequency) based on prior trials that have evaluated temperature manipulations, pH management, transfusion triggers, and pharmacologic strategies for improving neurologic complications of cardiac surgery . Postoperative MRI is not always feasible for reasons already discussed. According to our calculations, we will need to obtain MRI data on a total of 122 patients in each study arm (244 patients in total) to have 80% power to detect 40% reduction in the composite outcome of stroke, DWI lesion, or cognitive decline 4 to 6 weeks after surgery, assuming that 45% of Control Group patients experience adverse neurologic events. The Type I error is 5%.

Our current enrollment trajectory suggests that at least 277 patients will have undergone the protocol of our study before the end of the funding period for the initial grant. At that point we would expect to have 101 patients who have undergone MRI for evaluation of DWI lesions. An additional 143 patients with complete MRI, stroke, and cognitive endpoint data are needed to reach the target of 244 patients with the primary, complete endpoint data. To reach this target, we will need to enroll an additional 350 patients in this renewal. Our recruitment projections for our initial funded study are a conservative estimate, as we have enrolled 277 patients to our study (101 have MRI data). On average, 5 to 8 patients are enrolled per month. These projections confirm that the plan for this submission of studying 350 additional patients (a total of 630 patients) will ensure completion of the study with 244 patients having all study assessments, including MRI, at the completion of the proposed study funding period.

In addition, we calculated the minimal sample size required to detect 0.2 SD difference in combined Z-score for cognitive tests normalized to the control group's data between the Intervention and Control groups with 80% power . We assume 2 follow-up points (4 to 6 weeks and 1 year after surgery) and an average within-patient correlation of 0.7 (observed in our preliminary data). The calculations indicate that we will need 177 observations per group, or 354 patients in total, to detect 0.2 SD difference with 80% power (assuming 5% Type I error). The study (first and second funding periods) will recruit a total of 489 patients to meet the MRI endpoint. Therefore, we will meet our goal of having 354 patients to detect the expected 0.2 SD difference in combined cognitive score seven with a 1-year drop-out rates high as 27%. Historically, the drop-out rate for cognitive testing at 1 year in similar populations has been between 3% and 24% .

For Specific Aim 4, we assessed the level of statistical power to detect clinically meaningful differences in proportion of patients with postoperative delirium based on the sample size for Aim 1. Our preliminary data indicate a 50% reduction in this outcome when a structured instrument for delirium assessment is used (frequency of 33% vs. 66% in Intervention vs. Control Group). This marked decrease was based on n = 37 patients. Therefore, in the power assessment for this aim we conservatively assumed 50% frequency of delirium in the Control Group. We will expect to see a 40% reduction in frequency of this condition in the Intervention Group. Our calculations indicate that having a minimum of 122 patients in each group with thorough delirium assessments (not performed in all patients in the first cohort) will allow us to detect a 40% decrease in proportion of patients who develop delirium in the Intervention Group with 87% power, assuming a 5% level of statistical significance for the two-sided test. We have instituted careful delirium assessments in our current. Postoperative MRI is not always feasible for reasons already discussed. According to our calculations, we will need to obtain MRI data on a total of 122 patients in each study arm (244 patients in total) to have 80% power to detect 40% reduction in the composite outcome of stroke, DWI lesion, or cognitive decline 4 to 6 weeks after surgery, assuming that 45% of Control Group patients experience adverse neurologic events. The Type I error is 5%.

Our current enrollment trajectory suggests that at least 277 patients will have undergone the protocol of our study before the end of the funding period for the initial grant. At that point we would expect to have 101 patients who have undergone MRI for evaluation of DWI lesions. An additional 143 patients with complete MRI, stroke, and cognitive endpoint data are needed to reach the target of 244 patients with the primary, complete endpoint data. Our recruitment projections for our initial funded study are a conservative estimate, as we have enrolled 277 patients to our study (101 have MRI data). On average, 5 to 8 patients are enrolled per month. These projections confirm that the plan for this submission of studying 350 additional patients (a total of 630 patients) will ensure completion of the study with 244 patients having all study assessments, including MRI, at the completion of the proposed study funding period.

As of June 2016, we have enrolled 280 patients in the first five years and 244 patients in the second five year study. We need approximately 150 patients to complete enrollment.

In addition, we calculated the minimal sample size required to detect 0.2 SD difference in combined Z-score for cognitive tests normalized to the control group's data between the Intervention and Control groups with 80% power. We assume 2 follow-up points (4 to 6 weeks and 1 year after surgery) and an average within-patient correlation of 0.7 (observed in our preliminary data). The calculations indicate that we will need 177 observations per group, or 354 patients in total, to detect 0.2 SD difference with 80% power (assuming 5% Type I error). The study (first and second funding periods) will recruit a total of 489 patients to meet the MRI endpoint. Therefore, we will meet our goal of having 354 patients to detect the expected 0.2 SD difference in combined cognitive scores even with a 1-year drop-out rate as high as 27%. Historically, the drop-out rate for cognitive testing at 1 year in similar populations has been between 3% and 24%.

For Specific Aim 4, we assessed the level of statistical power to detect clinically meaningful differences in proportion of patients with postoperative delirium based on the sample size for Aim 1. Our preliminary data indicate a 50% reduction in this outcome when a structured instrument for delirium assessment is used (frequency of 33% vs. 66% in Intervention vs. Control Group). This marked decrease was based on n = 37 patients. Therefore, in the power assessment for this aim we conservatively assumed 50% frequency of delirium in the Control Group. We will expect to see a 40% reduction in frequency of this condition in the Intervention Group. Our calculations indicate that having a minimum of 122 patients in each group with thorough delirium assessments (not performed in all patients in the first cohort) will allow us to detect a 40% decrease in proportion of patients who develop delirium in the Intervention Group with 87% power, assuming a 5% level of statistical significance for the two-sided test. We have instituted careful delirium assessments in our current protocol. Thus, our sample size projections are conservative estimates, as we will have at least 60 patients in each group with careful delirium assessments by the completion of the first 5 years of the study. At the completion of the second 5 years, we are likely to have 180 patients in each study treatment arm with careful delirium assessments.

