**Table 2. Summary of Study Timeline During the Initial Phase of the Project**

We will continue this study for an additional 5-years that will enroll 350 new patients (in addition to the 280 patients of the initial study) over a 45-month period (~8 patients/month) with the remaining duration of the proposed funding used for patient follow-up testing, data analysis, manuscript preparation, and dissemination of the results. As of June 2016, we have enrolled 280 patients in the first five years and 244 patients in the second five year study. We need approximately 150 patients to complete enrollment.

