## Feasibility of Recruitment and Retention

The investigative team has a track record of high enrollment in industry-sponsored and extramurally funded clinical trials in patients undergoing cardiac surgery. The original study end point of 280 patients over a 56-month enrollment period required approximately 5 to be enrolled each month. The study endpoint of 350 patients in the second phase of the study requires enrollment of approximately 8 patients/month, a rate that we feel is attainable based on our success in the first phase of the study. The volume of surgical procedures performed at Northwestern Memorial Hospital (Table 6) will allow for the study to be completed in the planned timeframe. Procedures for retention of patients in the study will include visits by the nurse coordinators to the patients during hospitalization to reinforce the importance of the study. The patients will be contacted by phone before the 4-to-6-week postoperative visit to confirm their testing session.

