### **NUMBER OF LOCAL PARTICIPANTS:**

150 participants

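### The sample size text gives two incompatible enrolment totals, 630 and 489, for the same 244-patient target, and neither delivers 244 at the MRI yield printed beside them

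*Combined protocol and SAP*

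**What the plan says.** The sample size text (under Rapid Dissemination of Clinical Research, after the line introducing the statistical plan) sets the target at 122 patients per arm, 244 in all. This is for 80% power at a two-sided 5% level with a 45% control rate and a 40% relative reduction. It expects an intervention rate of 25% to 27%.

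From there it gives three accounts of enrolment:

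- **630.** The first phase is described as "as we have enrolled 277 patients to our study (101 have MRI data"). The remaining need is then stated: "An additional 143 patients with complete MRI, stroke, and cognitive endpoint data are needed to reach the target of 244 patients". The plan answers it with "To reach this target, we will need to enroll an additional 350 patients in this renewal", and concludes that "the plan for this submission of studying 350 additional patients (a total of 630 patients) will ensure completion of the study with 244 patients" with all assessments. Feasibility of Recruitment and Retention repeats the 350: "The study endpoint of 350 patients in the second phase of the study requires enrollment of approximately 8 patients/month".
- **489.** The paragraph on the cognitive Z-score, which appears twice, says the two funding periods together will recruit 489 patients for the MRI requirement. It rests the tolerated 27% one-year drop-out on that number.
- **June 2016 update.** The timeline section and the sample size text both report: "As of June 2016, we have enrolled 280 patients in the first five years and 244 patients in the second five year study". They add: "We need approximately 150 patients to complete enrollment". The section on local participants also gives "150 participants".

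The 244 enrolled in the second phase and the 244-patient target are different quantities that happen to coincide.

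**The concern.** A reader, a monitoring board or a review committee should find one number that says when enrolment is complete, and the yield behind it. Here 630 and 489 are both explicitly attached to the same target, and they differ by 141 patients. The June 2016 figures agree with neither: 489 had already been exceeded, and under the 350-patient plan 106 patients would remain, not about 150.

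The plan also treats 630 as a guarantee, although the yield in the same paragraph does not support it. The target is defined by complete MRI, stroke and cognitive data, but the progress count subtracted from it (101) is described only as patients with MRI. At stake are the stopping point for enrolment, the power for the primary comparison and the basis of the drop-out allowance.

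**Working it through.** **1. Reproduce the target.** Inputs from the sample size text: p1 = 0.45, p2 = 0.27, d = 0.18, mean p = 0.36, two-sided 5%, 80% power, equal arms.

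- Uncorrected: n = [1.960 × √(2 × 0.36 × 0.64) + 0.8416 × √(0.45 × 0.55 + 0.27 × 0.73)]² / 0.18² = (1.3305 + 0.5612)² / 0.0324 = 110.4, so 111 per arm.
- Continuity-corrected: n′ = (n/4) × [1 + √(1 + 4/(n × d))]² = (110.4/4) × (1 + √1.201)² = 121.3, so 122 per arm.

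The plan's 122 per arm therefore reproduces with a continuity correction. Its 87% delirium power (50% v 30%, 122 per arm) points the same way: 86.9% corrected, 89.5% uncorrected. The plan does not state the correction, so I show both versions below.

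**2. Yield.** 101/277 = 36.5%.

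**3. What each total delivers at that yield.**

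| Enrolment | Source | Expected MRIs | Against 244 |
|---|---|---|---|
| 489 | printed | 489 × 0.3646 = 178 | 66 short |
| 630 | printed | 101 + 350 × 0.3646 = 101 + 127.6 = 229 | 15 short |
| about 674 | 280 + 244 + about 150, not printed as a sum | 674 × 0.3646 = 246 | 2 over |

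The plan uses both 277 and 280 for the first phase. Applying the yield to all 630 gives 229.7, which makes no material difference.

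**4. Yield each printed total would need.**

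- 630: 143/350 = 40.9% from the new patients.
- 489: 489 − 277 = 212 new patients, and 143/212 = 67%.
- At 36.5%, 244 MRIs need 244/0.3646 = 669 enrolled.

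**5. The update against the 350 plan.** 280 + 244 = 524 enrolled, and 350 − 244 = 106 remaining, against about 150 stated.

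**6. Power with 229 patients (114.5 per arm), before any missing cognitive tests.** Power = Φ{[d√n − 1.960√(2 × mean p × (1 − mean p))] / √(p1(1 − p1) + p2(1 − p2))}. The corrected version uses the n that the continuity formula maps to 114.5, which is 103.7 at 27%.

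| Comparison | Corrected | Uncorrected |
|---|---|---|
| 45% v 27%, 244 patients | 80% | 84% |
| 45% v 27%, 229 patients | 77% | 81% |
| 45% v 25%, 229 patients | 86% | 89% |

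**7. Complete data.** Every patient with complete data has an MRI, but not the reverse, so the MRI counts are upper bounds. Experimental Problems expects some missed 4 to 6 week testing, and Missing data rules out imputing outcomes. The documents give no rate. As an assumption, take 0% to 10% of MRI patients lacking the test. At the 10% end:

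- 630 gives 0.9 × 229.7 = 207 complete, with power for 45% v 27% of 73% corrected and 77% uncorrected.
- 674 gives 0.9 × 245.8 = 221 complete, with 76% and 80%.

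**8. Drop-out allowance.** 354 patients are needed: 1 − 354/489 = 27.6%, which is the plan's 27%. With all enrolled patients in the denominator, 1 − 354/524 = 32% and 1 − 354/630 = 44%.

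**The case against.** **The gap has been closed.** The 277/101/350/630 wording is forward-looking renewal text, and the June 2016 statement is later. Its implied total of about 674 gives about 246 MRIs. This stands as far as it goes. A reader might infer that the trial is planned 15 MRIs short, and the documents do not support that, because their latest statement roughly covers the MRI target. A reader might also infer that three totals are tied to 244. Only 630 and 489 are; the update speaks of completing enrolment and names no MRI count. What remains is that the older totals are still in the current text, unreconciled.

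**A higher yield is on record.** The section COx and Clinical Outcomes reports MRI in 82 of 176 patients (46.6%). At that rate 350 more would give 163, or 264 in total. But this is an earlier and smaller count, and the plan's projection uses the later 101 of 277. The fall between the two makes a guarantee harder to defend, and it is a reason not to treat the yield as constant.

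**Power barely moves.** Without the correction, or at the 25% end of the expected range, 229 patients still exceed 80%. This is fair: the 77% figure needs both the inferred correction and the 27% rate.

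**The 489 error is harmless.** For the retention claim this is true. A larger total tolerates more drop-out, so the conclusion does not fail.

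**Conclusion.** The inconsistency is real, and the figures are wrong as written. The plan gives 630 and 489 for one target, and at its own adjacent yield they deliver about 229 and 178 MRIs, not 244. The claim that 630 ensures 244 needs a 40.9% yield that is not stated for the renewal.

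The weight of the point lies in the missing single total, not in a large loss of power. At 45% v 27% the loss with 229 patients is about 3 points before any missing cognitive data (80% to 77% corrected, 84% to 81% uncorrected). It is larger with missing data, for which the plan states no allowance. The figure implied by the update, about 674, meets the MRI count with about 2 patients to spare, so it leaves almost nothing for missed 4 to 6 week tests.

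These results assume that the 36.5% yield continues. The corrected power figures also assume that the plan used the continuity correction that reproduces its 122 per arm.

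**What to change.** In the timeline section, the sample size text and Feasibility of Recruitment and Retention, state one enrolment total with its assumed complete-endpoint yield. Take that yield from the actual number, pooled over arms, with complete MRI, stroke and cognitive data among the 524 enrolled by June 2016.

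If 630 is kept instead, say that it is expected to give about 229 MRIs. Give the power with it: about 77% corrected or 81% uncorrected for 45% v 27%, and about 86% or 89% for 45% v 25%, before missing cognitive data.

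In either case:

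- remove the wording that 630 ensures 244;
- delete 489;
- recompute the tolerated one-year drop-out from the reconciled total (about 32% at 524, 44% at 630).

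The cost is a text correction and one pooled count from data already held, with no unblinding. Whether more patients than the June 2016 projection are needed depends on that count.
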